#### **1.3.4. Exploratory efficacy analyses**

Exploratory efficacy analyses will be conducted to investigate the potential effect of treatment on:

1. SBPnight
2. DBPnight
3. Average daytime (9:00 to 21:00) ambulatory diastolic blood pressure (DBPday)

These analyses will include two-sample t-tests to test one-side hypotheses of superiority for pairwise comparisons between treatment arms 1 and 2, 1 and 3, and 2 and 3.

Further, two-sample t-tests to test one-side hypotheses of superiority for pairwise comparisons between treatment arms 1 and 3 and 2 and 3 will be performed for SBPday, SBP24h, and DBP24h. The comparison of treatment arms 1 and 2 for these endpoints are covered separately under the respective primary and secondary efficacy analyses.

All exploratory efficacy analyses will be conducted on the ITT population including LOCF (and MMRM if possible) for subjects who were withdrawn from treatment early. Sensitivity analyses will be used to compare these results to those of the PP data set.

#### **1.3.5. Definition of one-sided confidence interval (CI)**

For clarity, the non-inferiority trial will be based on comparing the change from baseline to end of study for the OE amlodipine besylate tablet and OE celecoxib capsule arm (treatment arm 1) minus 0.5 \* the OE amlodipine besylate tablet and matched placebo for OE celecoxib capsule arm (treatment arm 2) with 0. A one-sided 97.5% CI for  $\delta$  will be computed. This is consistent and equivalent with the hypothesis section of the protocol, which states that the primary efficacy endpoint will be that the lower limit of the 95% CI for SBPday reduction in treatment arm 1 will be at least 50% of the mean reduction in treatment arm 2. This statement is to clear up places in the protocol and SAP that conceptually state the comparison in less technical language.

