

Statistical Methods for Primary Efficacy Analysis:
	
The primary efficacy endpoint for this trial will be the difference in the mean reduction in SBP_{day} from Day 0 to Day 14 between subjects treated with amlodipine tablets (10 mg) and celecoxib capsules (200 mg) given together (arm 1) and amlodipine tablets (10 mg) given alone (with matched celecoxib placebo) (arm 2), and specifically that the lower limit of the 95% confidence interval for the arm 1 subjects is at least 50% of the mean reduction in the arm 2 subjects.
 
A two-sample t-test will be used to test the one-sided hypothesis that treatment with amlodipine tablets (10 mg) and celecoxib capsules (200 mg) given together (arm 1) is non-inferior to the control treatment with amlodipine tablets (10 mg) given alone (with matched celecoxib placebo) (arm 2).
 $H_0: \Delta SBP_{day,1} - 0.5(\Delta SBP_{day,2}) \geq 0$ $H_1: \Delta SBP_{day,1} - 0.5(\Delta SBP_{day,2}) < 0$ 
Where $\Delta SBP_{day,1}$ is the reduction in SBP_{day} for subjects in arm 1. $\Delta SBP_{day,2}$ is the reduction in SBP_{day} for subjects in arm 2.
 
For the primary analysis, an intent-to-treat (ITT) data set will be used comprising of randomized subjects with a valid ABPM measurement from Day -1 to Day 0 and also either a valid ABPM measurement from Day 13 to Day 14, where a subject completes the 14-day treatment plan, or a valid ABPM measurement from Day 6 to Day 7, where a subject is withdrawn from treatment at Day 7 because of an SBP_{24h} > 169 mmHg and/or a DBP_{24h} > 110 mmHg.

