10.2 Statistical Analysis of Efficacy Data

10.2.1 Primary Efficacy Endpoint

The primary efficacy endpoint for this trial will be the difference in the mean reduction in SBP_{day} from the baseline (Day –1 to Day 0) ABPM measurement to the final (Day 13 to Day 14) ABPM

measurement, where a subject completes the 14-day treatment plan, or to the Day 6 to Day 7 ABPM measurement, where a subject is withdrawn from treatment at Day 7, between subjects treated with amlodipine tablets (10 mg) and celecoxib capsules (200 mg) given together (arm 1) and amlodipine tablets (10 mg) given alone (i.e., with matched celecoxib placebo) (arm 2).

The primary efficacy endpoint will be that the lower limits of the 95% confidence interval for SBP_{day} reduction in treatment arm 1 will be at least 50% of the mean reduction in treatment arm 2.

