10.2.3 Primary Efficacy Endpoint Analysis

A two-sample t-test will be used to test the one-sided hypothesis that treatment with amlodipine tablets (10 mg) and celecoxib capsules (200 mg) given together (arm 1) is non-inferior to half of the effect achieved with the control treatment with amlodipine tablets (10 mg) given alone (with matched celecoxib placebo) (arm 2).

$$H_0: \Delta SBP_{day,1} - 0.5(\Delta SBP_{day,2}) \geq 0 \text{ mmHg}$$

$$H_1: \Delta SBP_{day,1} - 0.5(\Delta SBP_{day,2}) < 0 \text{ mmHg}$$

Where $\Delta SBP_{day,1}$ is the change, for subjects in arm 1, in the SBP_{day} from the baseline ABPM measurement ($SBP_{day,1,0}$) to the final ABPM measurement ($SBP_{day,1,14}$).

$$\Delta SBP_{day,1} = SBP_{day,1,0} - SBP_{day,1,14}.$$

$\Delta SBP_{day,2}$ is the change, for subjects in arm 2, in SBP_{day} from the baseline ABPM measurement ($SBP_{day,2,0}$) to the final ABPM measurement ($SBP_{day,2,14}$).

$$\Delta SBP_{day,2} = SBP_{day,2,0} - SBP_{day,2,14}.$$

Refer to Appendix H for further details regarding the efficacy analysis, and in particular the non-inferiority margin.

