10.9 Sample Size

- 1) The sample size is to be based on the hypothesis that the mean reduction in SBP_{day} from Day 0 to Day 14 of subjects treated with amlodipine tablets (10 mg) and celecoxib capsules (200 mg) given together (arm 1) minus half the mean reduction in SBP_{day} from Day 0 to Day 14 of subjects treated with amlodipine tablets (10 mg) given alone (with matched celecoxib placebo) (arm 2) is at least 0.
- 2) Formula

Sample size is based on the formula

$$n = \left\lceil 2 \left(\frac{Z_{1-\alpha} + Z_{1-\beta}}{d} \right)^2 s^2 \right\rceil$$

where

s is the standard deviation (8.7)

d is the anticipated mean difference (6.2)

α is the one-sided level of significance (0.05)

$1-\beta$ is the power, one-sided (80%)

$\lceil \rceil$ is the ceiling function

3) Margin

The margin is based on a mean reduction of 8.8 mmHg in SBP_{day} for the Amlodipine+Placebo group and a mean reduction of 10.6 mmHg for the Amlodipine+Celecoxib group as seen in the previous study, KIT-302-03-01. To ensure that at least half the effect is maintained, a value of $10.6 - 0.5(8.8) = 6.2$ mmHg should be set for d .

4) Standard Deviation

The standard deviation is based on an 8.1 mmHg standard deviation for the Amlodipine+Placebo group and a 9.2 mmHg standard deviation for the Amlodipine+Celecoxib group in the previous study (KIT-302-03-01). The pooled standard deviation for the power and sample size justification is 8.7 mmHg.

5) Loss to Follow-up Adjustment

The final sample size is rounded up to allow for a loss to follow-up. The study selected a round number at least 10% larger than the number necessary to protect against potential subjects not fully participating in the entire trial.

Refer to Appendix H for further details regarding the determination of sample size.

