### **7.7. Primary Efficacy Analysis**

The primary efficacy analysis is to establish the non-inferiority of amlodipine tablets (10 mg) and celecoxib capsules (200 mg) given together (arm 1) with half the effect achieved with amlodipine tablets (10 mg) given alone (celecoxib placebo) (arm 2).

Statistics are based on the change in BP from the baseline ABPM measurement (Day -1 to Day 0) to the post-dose ABPM measurement (Day 13 to Day 14 or if a LOCF is required Day 6 to Day 7), as this represents the efficacy of the treatment. As indicated below, the change will be Day 13 to Day 14 minus Baseline and so a reduction will be a negative number. Sensitivity analysis will compare the results for the ITT population with those of the PP dataset and an MMRM analysis, if possible. A sensitivity analysis will also compare the results with the mITT population.

The hypothesis test being conducted is as follows:

$$H_0: \Delta SBP_{day,1} - 0.5(\Delta SBP_{day,2}) \geq 0 \text{ mmHg}$$

$$H_1: \Delta SBP_{day,1} - 0.5(\Delta SBP_{day,2}) < 0 \text{ mmHg}$$

Where  $\Delta SBP_{day,1}$  is the change, for subjects in arm 1, in the  $SBP_{day}$  from the baseline ABPM measurement ( $SBP_{day,1,base}$ ) to the final ABPM measurement ( $SBP_{day,1,14}$ ).

$$\Delta SBP_{day,1} = SBP_{day,1,14} - SBP_{day,1,base}.$$

$\Delta SBP_{day,2}$  is the change, for subjects in arm 2, in  $SBP_{day}$  from the baseline ABPM measurement ( $SBP_{day,2,0}$ ) to the final ABPM measurement ( $SBP_{day,2,14}$ ).

$$\Delta SBP_{day,2} = SBP_{day,2,14} - SBP_{day,2,base}.$$

This makes the actual test statistic:

$$\delta = \Delta SBP_{day,1} - 0.5(\Delta SBP_{day,2})$$

A one-sided 97.5% CI for  $\delta$  will be computed. In addition, a two-sided non-inferiority t-test comparing  $\delta$  to 0 will provide an appropriate p-value. This p-value will be computing the probability of observing a value  $\geq 0$  from a normal distribution for  $\delta$ .

Refer to the protocol Appendix H for further details regarding the efficacy analysis, and in particular the non-inferiority margin.

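### SAP 1.3.5 calls two different primary success rules equivalent: the protocol's arm-1-only interval ignores arm 2's sampling error (about 3.6% one-sided type I error), while the SAP's interval for delta holds 2.5%

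*SAP*

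**What the plan says.** The documents give the primary criterion in two forms.

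- **Arm 1's own interval.** Protocol 10.2.1 puts it this way: "lower limits of the 95% confidence interval for SBP_{day} reduction in treatment arm 1 will be at least 50% of the mean reduction"; the reduction meant at the end is arm 2's. The synopsis, under the primary efficacy methods, has: "lower limit of the 95% confidence interval for the arm 1 subjects is at least 50% of the mean reduction in the arm 2". Neither place says whether the 95% interval is one- or two-sided.
- **A contrast of both arms.** Protocol 10.2.3 states: "A two-sample t-test will be used to test the one-sided hypothesis that treatment" in arm 1 is non-inferior to half the arm 2 effect, with hypotheses on the arm 1 change minus half the arm 2 change. SAP 7.7 makes that contrast, delta, the test statistic: "A one-sided 97.5% CI for" delta is to be computed, with a p-value against 0.

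SAP 1.3.5 adopts the interval for delta and then comments: "This is consistent and equivalent with the hypothesis section of the protocol". It goes on to describe that section by the arm-1 interval criterion. It adds that the aim is to tidy up places where the comparison is put less technically.

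**The concern.** An interval for arm 1 alone carries only arm 1's sampling error. Comparing its limit with half of arm 2's mean treats that mean as a fixed number, although it is estimated from a group of the same size. An interval for delta carries both sources of error. The arm-1 rule should therefore be easier to pass than the SAP's rule, with a type I error above 2.5%.

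At stake is the trial's single confirmatory decision, on which all confirmatory claims for the secondary endpoints depend (Protocol 10.2.5, SAP 1.3.18). If both rules stand and the SAP vouches that they agree, a result between them could be called a success under the protocol and a failure under the SAP.

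**Working it through.** **Inputs.** SDs are 9.2 mmHg (arm 1) and 8.1 mmHg (arm 2), from Protocol 10.9 and Appendix H.3. There are 45 per arm (Appendix H.4). D1 and D2 denote observed mean reductions, with positive values favourable.

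**The plan's own figures.** 10.6 − 0.5 × 8.8 = 6.2 mmHg. √[(9.2² + 8.1²)/2] = 8.67, which rounds to 8.7. 105 × 3/7 = 45 per arm. All three reproduce. The preliminary 27 per group in Appendix H.4 does not: its stated inputs give 31. That is a separate matter and does not affect this point.

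**Standard errors**

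- Arm 1 alone: 9.2/√45 = 1.371.
- Delta: √(9.2² + 0.25 × 8.1²)/√45 = √(84.64 + 16.40)/√45 = 1.498, about 9% larger.

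**Type I error of the arm-1 rule, read as a two-sided 95% interval.** At the boundary, true D1 equals half of true D2. The rule passes when D1 − 0.5·D2 exceeds 1.96 × SE(arm 1). The true standard error of that difference is SE(delta), so the effective critical value is 1.96 × 1.371/1.498 = 1.79, and P(Z > 1.79) = 3.6%.

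| SDs (arm 1 / arm 2) | Arm-1 rule, normal | Arm-1 rule, simulated | 97.5% CI for delta, simulated |
|---|---|---|---|
| 9.2 / 8.1 | 3.64% | 3.57% | 2.48% |
| 8.7 / 8.7 | 3.98% | 3.92% | 2.50% |

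The simulations used 1,000,000 trials at 45 per arm, estimated SDs, t quantiles, and Welch degrees of freedom for delta. Sample size hardly matters: the t-based figure for 9.2/8.1 is 3.56% at 27 per arm and 3.59% at 45. The SD ratio matters more. If s2/s1 is assumed to lie between 0.5 and 1.5, the error runs from 2.9% to 5.8%.

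**Where the rules disagree, at the planning SDs**

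- Arm-1 rule passes above t(44) × 1.371 = 2.015 × 1.371 = 2.76 mmHg.
- Delta rule, Welch variance, passes above t(60) × 1.498 = 2.000 × 1.498 = 3.00 mmHg.
- Delta rule, pooled variance: SE = 8.67 × √1.25/√45 = 1.445, so it passes above t(88) × 1.445 = 1.987 × 1.445 = 2.87 mmHg.

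The gap is 2.76 to 3.00 mmHg under Welch, and 2.76 to 2.87 mmHg under pooling.

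**Chance of landing in the Welch gap.** If the true difference is 6.2: Φ((3.00 − 6.2)/1.498) − Φ((2.76 − 6.2)/1.498) = Φ(−2.14) − Φ(−2.30), about 0.5%. At the null boundary: Φ(2.00) − Φ(1.84), about 1%.

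**Direction of the bound.** SAP 1.3.7 codes change as endpoint minus baseline, so benefit means delta below 0 and success needs the upper limit below 0. SAP 2.3 asks for the lower limit to be below 0. Read literally, that is met about 97.5% of the time at the null boundary (simulated 0.975). SAP 1.3.5 and 7.7 do not name the bound.

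**The case against.** The strongest reply is that the SAP already runs the right analysis. Sections 1.3.5 and 7.7 rest on delta, and no SAP section plans an arm-1-only interval. Section 1.3.5 sits under Changes from Protocol and describes itself as clarification. The protocol's formal hypotheses in 10.2.3 also involve both arms, so the interval for delta does match the protocol's test. The arm-1 sentence can then be taken as a loose paraphrase. A result in the gap is improbable, and calling it a success would mean disregarding SAP 1.3.5 and 7.7.

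Most of this stands, and it limits the severity. It does not rescue the equivalence claim. The sentence in Protocol 10.2.1 names the interval, its level, the arm and the threshold, under the primary endpoint heading. It can be applied only with arm 2's observed mean, since the true mean is unknown. Section 1.3.5 cites exactly that criterion, and although it is listed as a change it says that nothing has changed.

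Three stronger readings are tempting, and the documents do not support them.

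- *The primary analysis has inflated error.* It does not. The 3.6% belongs to the protocol's interval wording, and the planned interval for delta holds 2.5%.
- *The error is 6.5% instead of 2.5%.* A one-sided 95% reading of the arm-1 rule does give about 6.5%, but its nominal level is 5%. The comparison mixes the missing arm 2 variance with a different alpha. SAP 1.3.11 calls the one-sided 0.05 in Protocol 10.9 an error, and Appendix H uses 0.025.
- *Arm 1's interval is always the narrower.* That holds for a Welch variance. With a pooled variance at 45 per arm it fails once s2 is below about 0.80 × s1. The prior-study ratio is 8.1/9.2 = 0.88. Neither document says which variance applies.

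**Conclusion.** The point holds as a should-fix, not a must-fix. The primary success criterion is written in two forms that are not equivalent, and SAP 1.3.5 says that they are. The protocol form, read as a two-sided 95% interval, has about 3.6% one-sided type I error with SDs 9.2/8.1 and about 4% with 8.7 in both arms. The two forms disagree over about 0.2 mmHg of observed difference under a Welch variance, and about 0.1 mmHg under pooling. These figures assume equal arms of 45 and the prior study's SDs.

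No planned estimate, p-value or sample size is wrong on this account. What needs correcting is a false statement about the confirmatory rule, a variance for delta that is never stated, and a bound in SAP 2.3 that points the wrong way. SAP 1.5 labels the current version as post-unblinding, which makes a single unambiguous rule more valuable. A reader might infer that the equivalence sentence was added after unblinding; the documents do not show whether it was in the pre-unblinding version.

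**What to change.** In SAP 1.3.5, remove the sentence beginning "This is consistent and equivalent with the hypothesis section of the protocol" and state instead that:

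- the one-sided 97.5% confidence interval for delta replaces the arm-1-only interval rule in Protocol 10.2.1 and the synopsis;
- it is the sole criterion for primary success;
- the arm-1-only rule will not be used to claim success.

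In SAP 7.7, give the variance and degrees of freedom for delta, for example s1²/n1 + 0.25 × s2²/n2 with Satterthwaite degrees of freedom. A pooled variance would also be a definite choice if it is named.

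In SAP 2.3 and 7.7, state the bound to match endpoint-minus-baseline coding: success if the upper limit for delta is below 0.

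The cost is wording only, with no new data and no change to the sample size. At the planning SDs the success threshold is about 0.2 mmHg above that of the literal protocol wording (3.00 against 2.76 mmHg, Welch variance).

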#### **1.3.6. Analysis populations**

In addition to adding the mITT population noted above, a Randomized population (defined as all randomized subjects) will be added to produce all listings, except for screening failures and the listing of plasma amlodipine concentrations. The Randomized population will also be used to produce a summary tabulation of the number and percentage of subjects who completed the study and who discontinued the study after randomization by treatment arm and overall, and the number and percentage of patients with a given primary reason for discontinuation (AE, withdrawal of consent, lost to follow-up, protocol violation, study terminated, or other) by treatment arm and overall. The Randomized population will also be used to produce a summary tabulation of the number of subjects in the randomized population, the ITT population, the mITT population, the PP population, the safety population, and the PK population.

An Overall Trial population (defined as all patients screened) will be added and used to produce the listing of screening failures, as well as a tabular summary of the number of patients at Initial Screening Visit, number of patients at Final Screening Visit, number of patients at Day 0 visit,

number of patients randomized, and number of patients at each of the remaining study visits (Days 6, 7, 13, 14 and 28) by treatment arm and overall.

The protocol includes a PK assessment at Day 14 for subjects enrolled at Investigational Sites that have ultraviolet- (UV-) shielded lights; however, a formal definition of the PK population for analysis was not included in the protocol. A definition of the PK population was added to the SAP (see Section 4.1). The listing of plasma amlodipine concentrations will use all subjects that were enrolled at an Investigational Site that had UV-shielded lights, and the PK population will be used for all analyses (tabular summaries and box plot).

### **1.3.7. Definition of change from baseline**

For all efficacy endpoints, the mean change will be computed considering the difference between the value at endpoint and the value at baseline (Endpoint minus Baseline). The protocol states the mean change as baseline minus endpoint. This change does not affect the absolute value of the results but gives a more intuitive interpretation of the direction of change (i.e., with a negative value indicating a decrease in BP over time and a positive value indicating an increase in BP over time).

### **1.3.8. Peak and trough analyses**

SBP and DBP at the expected peak and trough times for amlodipine for the ITT population at Day 6 and Day 13 will be summarized by treatment arm by descriptive statistics. Additionally, the difference between Day 6 and Day 13 will be summarized by treatment arm by descriptive statistics, and compared between treatment arms using t-test. No last observation carried forward (LOCF) will be used for this analysis. Details of how peak and trough measurements will be selected from the ABPM measurements are included in Section 7.10.

### **1.3.9. Safety analyses**

#### **a. Oedema events**

A safety table extracting the occurrences of oedema events, which include treatment emergent adverse events (TEAEs) with preferred terms (PTs) of oedema, oedema peripheral, peripheral swelling, swelling, and joint swelling, from the adverse events table will be produced. See Section 7.9 for further detail. The rates of oedema events for treatment arms 1 and 2 will be reported and compared using exact logistic regression, reporting the odds ratio. The Fisher's exact test will be run to compare the number of oedema events that occurred while on treatment (Day 0 to Day 14+1) and post-treatment (>Day 14+1) between treatment arms 1 and 2.

#### **b. Other PTs of interest**

The protocol specified a comparison of AE rates for terms associated with hypotension, defined as dizziness, falls, light-headedness, and vertigo. The definition will be changed to TEAEs with PTs of orthostatic hypotension, fall, dizziness, dizziness postural, and vertigo. The use of PTs and the addition of orthostatic hypotension to the list provides a more precise and comprehensive analysis, as well as allows a direct comparison to a similar analysis conducted for the prior trial (KIT-302-03-01). Note, light-headedness is coded under dizziness as a PT.

#### **c. Adverse drug reaction (ADR)**

For the summary tabulations of TEAEs by assigned relationship to study drug, adverse reactions and suspected adverse reactions will be combined and presented as ADRs (i.e., pooled). The TEAE listing will continue to use the individual relationship assignments (i.e., adverse reaction, suspected adverse reaction, and unrelated), as specified in the protocol. The same approach was taken for the prior trial (KIT-302-03-01), and therefore, this change will allow for comparison across studies. A statistical evaluation of the rate of treatment-emergent ADRs among treatment arms using a Chi-

square test or Fisher's exact test (if more than 20% of the cells in a contingency table had expected counts less than 5) will be added.

**d. Unexpected adverse event (UAE)**

A tabulation of treatment-emergent UAEs (defined in Section 6.4) will be added. The summary will include the number of events, as well as the number and percentage of subjects. Subjects will be counted once per category [specific system organ class (SOC) or PT], regardless of the number of events that may have occurred for that patient in that category. The tabulation will be based on the respective **Principal Investigator (PI) assignments** of expectedness. A statistical evaluation of the rate of treatment-emergent UAEs among treatment arms using a Chi-square test or Fisher's exact test (if more than 20% of the cells in a contingency table had expected counts less than 5) will be performed.

As with the prior trial (KIT-302-03-01), there are several TEAEs designated as unexpected by one or more PIs for one or more subjects that the Sponsor considered as expected based on the product labelings for the study drugs, including dyspepsia, flatulence, vomiting, chest pain, pain (lower body pain), thirst, nasopharyngitis (cold symptoms), pharyngitis, sinusitis, alanine aminotransferase increased, increased appetite, arthralgia, back pain, joint swelling (swelling of knee), dizziness, headache, cough, epistaxis, dry skin, purpura, and rash.

Further, there were several TEAEs designated as expected by one or more PIs for one or more subjects that the Sponsor considered as unexpected as they were not listed in the product labelings for the study drugs and were not listed as expected AEs in the protocol, including toothache, seasonal allergy (hayfever symptoms), urinary tract infection, plantar fasciitis, dysphoria, epididymal cyst, blister, pigmentation disorder, feeling cold, and peripheral coldness. It should be noted that in the prior study (KIT-302-03-01), the Sponsor assigned pollakiuria as an unexpected event in error. Micturition frequency is listed in the labelings for both study drugs. As such, the Sponsor considers the pollakiuria events in this study and the prior study as expected.

The Sponsor's assignments of expectedness will be noted in the main body of the clinical study report, and a footnote will be added to the above tabular summary to clarify that it is based on the PI's assignments, which were not all consistent with the protocol-specified definition of UAE. A similar approach was taken for the prior trial (KIT-302-03-01), and thus will allow for comparison across studies. To facilitate the preparation of this text for the main body of the clinical study report, an analysis will be run based on the above expectedness changes (Sponsor's assignments), although, the table itself will not be included in the clinical study report.

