8.1.4 Expectedness of Adverse Events

An unexpected AE is one for which the nature or severity of the event is not consistent with the applicable study drug information (i.e., the most current version of the IB, the current product labeling for amlodipine tablets, and the current product labeling for celecoxib capsules) or listed in this protocol.

This study will enroll older subjects with existing hypertension. To that end, PTAEs and TEAEs can be expected due to the subjects' age and underlying conditions. These include: hypertension, hypertensive crisis, myocardial infarction, congestive heart failure, stroke both hemorrhagic and ischemic, any adult forms of cancer, and gastrointestinal ulcerations with complications including hemorrhage and perforation.

By definition, PTAEs initiate prior to administration of the first dose of study drugs, and thus a comparison against study drug specific risk information is inappropriate for determining expectedness of PTAEs. Thus, only AEs that can be expected due to subject age and underlying conditions are relevant for the expectedness determination for PTAEs.

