8.1.6 Routine Reporting of Adverse Events

PTAEs and TEAEs, whether or not associated with study drug administration, will be recorded on the AE form of the CRF and will be submitted to the Sponsor at regularly scheduled intervals.

The information to be entered in the CRF will include:

1. Medical diagnosis of the event in standard medical terminology (if a medical diagnosis cannot be determined, a description of each sign or symptom characterizing the event);
2. Date of onset of any new AE or the worsening of a previously observed AE. For the days when the subject is in the clinic, the time (based on a 24-hour clock) of onset should be recorded if available;
3. Date of resolution of the event (or confirmation ongoing). For the days when the subject is in the clinic, the time (based on a 24-hour clock) of resolution should be recorded if available;
4. Whether the event is serious (per definition in Section 8.1.1.2), and if so, the reason it is considered serious;
5. Severity of AE (per definitions in Section 8.1.2);
6. Assessment of the relationship of the AE to the study drug (per definitions in Section 8.1.3). Relationship assessments will only be made for TEAEs;
7. Whether the event is expected (per definition in Section 8.1.4);
8. Action taken in treating the AE (including concomitant medications or therapies administered) and/or change in study drug administration or dose (including whether the Study Drug was temporarily interrupted or discontinued);
9. Outcome of AE (recovered/resolved, recovered/resolved with sequelae, not recovered/not resolved, fatal, or unknown). Fatal should only be used when death is possibly related to the AE. If an outcome for an AE is not available at the time of the initial report, follow-up will proceed until an outcome is known or followed up to the final study visit. Any subject with a possible study drug-related TEAE at the final study visit will be followed until resolution or stabilization of the event. Further, any serious TEAE, whether or not related to study drugs that occurs within 14 days following the last dose of study drugs will be followed until resolution or stabilization of the event.

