### **UAE**

Per the protocol, an UAE is one for which the nature or severity of the event is not consistent with the applicable study drug information [i.e., the most current version of the Investigator's Brochure (IB), the current product labeling for amlodipine tablets, and the current product labeling for celecoxib capsules] or listed in the protocol (as provided below).

This study was to enroll older subjects with existing hypertension. To that end, PTAEs and TEAEs could be expected due to the subjects' age and underlying conditions. These include: hypertension, hypertensive crisis, myocardial infarction, congestive heart failure, stroke both hemorrhagic and ischemic, any adult forms of cancer, and gastrointestinal ulcerations with complications including hemorrhage and perforation.

By definition, PTAEs initiate prior to administration of the first dose of study drugs, and thus a comparison against study drug specific risk information is inappropriate for determining expectedness

of PTAEs. Thus, only AEs that can be expected due to subject age and underlying conditions are relevant for the expectedness determination for PTAEs.

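### The table and test of unexpected adverse events rest on investigator calls that the SAP says did not all follow the protocol definition, and the report will omit the planned table on the Sponsor's assignments

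*SAP*

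**What the plan says.** Protocol 8.1.4 sets one standard for all sites: "An unexpected AE is one for which the nature or severity of the event is not consistent with the applicable study drug information". The references are the Investigator's Brochure, the two product labels and a short list in the protocol of events expected from age and disease. Protocol 8.1.6 makes this a CRF item for every event: "Whether the event is expected (per definition in Section 8.1.4". SAP 6.4 repeats the definition.

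SAP 1.3.9 d adds a UAE tabulation that points to 6.4 for its definition but takes the investigators' assignments as data. It also adds a chi-square or Fisher's exact test among arms. SAP 7.9 includes UAEs in the TEAE category summary, which is tested the same way. SAP 7.3 sets two-sided 0.05 for safety tests.

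The same item records disagreement in both directions. Some terms were "designated as unexpected by one or more PIs for one or more subjects that the Sponsor considered as expected based on the product labelings", and others were "designated as expected by one or more PIs for one or more subjects that the Sponsor considered as unexpected". It says the investigators' assignments are ones "which were not all consistent with the protocol-specified definition of UAE".

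The planned handling has three parts. The Sponsor's assignments are described in the body of the study report. The investigator-based table carries a footnote. An analysis on the Sponsor's assignments is run to support that text, "although, the table itself will not be included in the clinical study report". The stated reason is comparability with KIT-302-03-01, which was handled similarly.

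**The concern.** A table labelled as unexpected events should count events that meet the definition of unexpected. This one counts events that an investigator marked that way, and the SAP says the two are not the same. The departures go both ways: events the Sponsor regards as labelled enter the table, and events it regards as unlisted drop out.

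The by-arm rates and p-value therefore do not measure the variable that SAP 6.4 defines. A reader of the report who wants to know whether the combination produced more events outside the known profile gets a caveat and a description. The plan does not promise the corrected counts by arm or a corrected test. That gap is avoidable, because the analysis that would narrow it is already to be run.

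**Working it through.** **1. Count of discrepant terms (SAP 1.3.9 d).**
- Unexpected to the investigator, expected to the Sponsor: dyspepsia, flatulence, vomiting, chest pain, pain, thirst, nasopharyngitis, pharyngitis, sinusitis, ALT increased, increased appetite, arthralgia, back pain, joint swelling, dizziness, headache, cough, epistaxis, dry skin, purpura, rash = 21.
- Expected to the investigator, unexpected to the Sponsor: toothache, seasonal allergy, urinary tract infection, plantar fasciitis, dysphoria, epididymal cyst, blister, pigmentation disorder, feeling cold, peripheral coldness = 10.
- Total 21 + 10 = 31 named terms. Both lists are introduced as examples, so they may be incomplete. The number of events or subjects affected is not given.

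**2. Are any of the 21 plainly in the labels?** Yes. Protocol Appendix G, section 6.1, Table 1 lists, for celecoxib, headache 15.8%, dyspepsia 8.8%, back pain 2.8% and rash 2.2%. Appendix F, section 6.1 gives dizziness 3.4% on amlodipine 10 mg. These figures show that the terms are listed, not that the drugs cause them: the celecoxib table is regardless of causality, and headache was 20.2% on placebo.

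**3. Definition against data source.**

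| Item | Protocol 8.1.4 / SAP 6.4 | Reported table, SAP 1.3.9 d |
|---|---|---|
| Standard | IB, two labels, protocol list | Investigator's CRF entry |
| Applied | Same references at every site | As each investigator judged |
| Agreement | – | Conceded to be partial |

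**4. What the disclosure covers.** The footnote is specified for the 1.3.9 d tabulation. Section 7.9 refers back to 1.3.9 d, but no footnote is stated for its TEAE category summary, which also tests UAEs. For the Sponsor-based analysis, the SAP does not say whether a between-arm test is included.

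**5. Direction of the effect (illustration only; the rates and error rates are assumptions).** Suppose the misclassification is unrelated to arm, with sensitivity se and false-positive rate fp. The recorded rate is q = se × p + fp × (1 − p), so the arm difference shrinks by the factor (se − fp). Take 105 subjects at the realised 6:6:1 (SAP 3.2): 105 × 6/13 = 48.5, say 48 per active arm. Power by the normal approximation, two-sided 0.05, arm 1 against arm 2:

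| Assumed true rates | se, fp | Recorded rates | Power |
|---|---|---|---|
| 30% vs 10% | none | 30% vs 10% | 69% |
| 30% vs 10% | 0.9, 0 | 27% vs 9% | 64% |
| 30% vs 10% | 0.7, 0.1 | 28% vs 16% | 29% |
| 30% vs 10% | 0.5, 0.2 | 29% vs 23% | 10% |
| 35% vs 10% | none | 35% vs 10% | 85% |
| 35% vs 10% | 0.9, 0 | 31.5% vs 9% | 79% |
| 35% vs 10% | 0.5, 0.2 | 30.5% vs 23% | 13% |

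Error of this kind dilutes a real difference and does not inflate the false-positive rate.

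**The case against.** The case for leaving the plan alone has real substance.

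- **The problem is disclosed.** A reader might infer that the corrected result is being concealed. The documents do not support that: the table is footnoted and the Sponsor's assignments go in the body of the report. What is missing is an assurance of corrected counts and a corrected test.
- **Only some assignments are in question.** A reader might infer that the investigators' calls are wrong throughout, or that sites contradicted one another on the same term. The SAP says only that not all calls fitted the definition. It describes investigators differing from the Sponsor, by one or more investigators for one or more subjects. Disagreement between investigators is a plausible inference but is not stated.
- **The Sponsor's list is not an error-free standard.** The SAP admits a Sponsor mistake over pollakiuria in the prior trial. It treats blister as unlisted, although the Medication Guide in Appendix G mentions blisters with fever. Its stated reasons cite the labels and the protocol list but not the IB, which is also in the definition and is not available here.
- **Expectedness is not fixed by term alone.** The definition covers nature or severity, so a labelled term can properly be unexpected in one subject. A rule set once per preferred term would lose that.
- **Blinding favours the investigators.** Site staff were blinded (Protocol 5.1.3). The Sponsor's reclassification stands in a SAP whose latest version is labelled post-unblinding (SAP 1.5), with no statement that it was made blind.
- **Other tables cover the events.** SAP 7.9 tabulates all TEAEs by system organ class, preferred term and severity, with separate SAE, ADR and oedema tables.

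These points rule out simply substituting the Sponsor's version for the investigators'. They do not justify leaving a definition-based table out of the report. Comparability with the prior trial is a reason to keep the investigator-based table, not to show it alone. It is also a limited reason, since the SAP indicates that the same kind of disagreement arose there.

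**Conclusion.** The point holds in a bounded form. As written, the plan reports a UAE table and test on a variable that the SAP concedes does not fully match its own definition. It also leaves out of the report the table on the Sponsor's assignments that it will already have produced.

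The size can be stated only as 31 named terms, 21 one way and 10 the other. The events, subjects and arms involved are not given. The power figures show direction under assumed rates and are not an estimate for this trial. A reader might also infer that site habits combined with unequal arm mix biased the comparison. SAP 3.2 acknowledges that the randomization ratio varied across sites, but it gives no ratios by site and says arms 1 and 2 stayed similar overall, so such a bias can be neither shown nor sized.

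The consequence is limited to an added safety table. Primary and secondary efficacy conclusions are unaffected.

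**What to change.** In SAP 1.3.9 d and 7.9:

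1. Include both UAE tables in the study report, each with events, subjects and percentages by arm and the between-arm test.
2. For the definition-based table, apply Protocol 8.1.4 in full (nature or severity, against the IB, both labels and the protocol list) in the same way across sites and arms. Have this done event by event by someone blind to treatment arm. If that is no longer possible, state that the reclassification was not blind.
3. Label the investigator-based table as the version for comparison with KIT-302-03-01, keep its footnote, and carry the footnote to the TEAE category summary in 7.9.
4. Draw any conclusion about unexpected events from the definition-based table, with the investigator-based table beside it.

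The cost is small but not nil. The Sponsor-based analysis is already planned, so the additions are one table in the report, some SAP wording and a documented review of expectedness that also covers severity and the IB. The comparison with the prior trial is kept.
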